#### Reporting of Excluded Values

Individual values excluded as outliers will be documented in the final report. Approval of the final report will connote approval of the exclusion.

#### **9.3.2 Pharmacokinetic Statistical Methodology**

PK parameters will be evaluated to estimate the relative bioavailability of the Test Formulation compared with the Reference Formulation. PK parameters will be summarized by treatment formulation and injection site.

Log-transformed  $C_{max}$ ,  $AUC(0-t_{last})$ , and  $AUC(0-\infty)$  parameters will be evaluated in a linear fixed-effects model with fixed effects for treatment formulation and injection-site location. The differences between the test and reference formulations will be back-transformed to present the ratios of geometric least squares means and the corresponding 90% CI.

Example SAS Code:

```
proc mixed data=xxx;
  by parameter;
  class formulation location;
  model log_pk = formulation location / residual;
  lsmeans formulation / alpha=0.1 cl pdiff;
  ods output lsmeans=lsmeans;
  ods output diffs=diffs;
run;
```

The  $t_{max}$  will be analyzed using a Wilcoxon rank sum test. Estimates of the median difference based on the observed medians, 90% CIs, and p-values from the Wilcoxon rank sum test will be calculated.

In addition, the following comparisons will be made:

- Test versus Reference separately at each injection site (injection site will be removed from the model above)
- Arm versus abdomen and thigh versus abdomen separately for each formulation (formulation will be removed from the model above)

Additional PK analyses may be conducted if deemed appropriate.

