### 3. INTRODUCTION

This SAP has been developed after review of the Clinical Study Protocol (final version dated 13 December 2019).

This SAP describes the planned analysis of the safety, tolerability and pharmacokinetic (PK) data from this study. A detailed description of the planned TFLs to be presented in the clinical study report (CSR) is provided in the accompanying TFL shell document.

The intent of this document is to provide guidance for the statistical and PK analyses of data. In general, the analyses are based on information from the protocol, unless they have been modified by agreement with Eli Lilly and Company. A limited amount of information concerning this study (e.g., objectives, study design) is given to help the reader's interpretation. When the SAP and TFL shells are agreed upon and finalized, they will serve as the template for this study's CSR.

This SAP supersedes the statistical considerations identified in the protocol; where considerations are substantially different, they will be so identified. If additional analyses are required to supplement the planned analyses described in this SAP, they may be performed and will be identified in the CSR. Any substantial deviations from this SAP will be agreed upon with Eli Lilly and Company and identified in the CSR. Any minor deviations from the TFLs may not be documented in the CSR.

This SAP is written with consideration of the recommendations outlined in the International Conference on Harmonisation (ICH) E9 Guideline entitled Guidance for Industry: Statistical Principles for Clinical Trials and the ICH E3 Guideline entitled Guidance for Industry: Structure and Content of Clinical Study Reports.

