## 5. STUDY DESIGN

Study AMBV is a Phase 1, subject-blind, investigator-blind, 2-arm, randomized, single-dose, parallel-design study in healthy subjects.

All subjects will be screened within 28 days prior to enrollment. Eligible subjects will be admitted to the clinical research unit (CRU) on Day -1 and randomized

- 1:1 to 2 treatment formulations and
- within each treatment formulation, 1:1:1 to 3 injection sites (arm, thigh, or abdomen)

using a computer-generated allocation code. On Day 1, subjects will receive a 2 x 1-mL (200 mg mirikizumab) SC dose of 1 of the following treatments according to the randomization schedule:

- 200 mg Mirikizumab Reference Formulation (100 mg/mL), 2 x 1-mL PFS
- 200 mg Mirikizumab Test Formulation (100 mg/mL), 2 x 1-mL PFS

The maximum total dose of mirikizumab a subject will receive is 200 mg.

Subjects may be allowed to leave the CRU after completing the 4-hour safety assessments on Day 1, at the investigator's discretion, and will return for PK and immunogenicity sampling and safety assessments at predefined times up to 12 weeks postdose. Subjects will be monitored for safety between outpatient visits by way of telephone assessment. Subjects will participate in the study for up to 12 weeks after last dose.

Safety and tolerability will be assessed through clinical laboratory tests, vital sign measurements, recording of adverse events (AEs), physical examination, and immunogenicity. At prospectively defined time points, injection-related assessments will be made including a VAS pain score.

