## 7. SAMPLE SIZE JUSTIFICATION

Up to 60 subjects may be enrolled to ensure that 48 subjects (24 subjects per treatment formulation with approximately 8 subjects per treatment formulation and injection site [arm, thigh, or abdomen]) complete the study.

Based on previous trials, it is expected that the coefficient of variation for area under the concentration versus time curve (AUC) and  $C_{max}$  to be approximately 40%. A sample size of 48 completed subjects (24 subjects per treatment formulation) will provide >90% probability that the limits of the 90% confidence interval (CI) for the ratio of geometric means will be within 24% of the estimate.

Subjects who are randomized but not administered any treatment formulation may be replaced to ensure that 48 subjects (24 per treatment formulation) complete the study.

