## 8. DEFINITION OF ANALYSIS POPULATIONS

The “Safety” population will consist of all enrolled subjects who received at least one dose of mirikizumab, regardless of whether they complete all protocol requirements.

The “Pharmacokinetic” population will consist of all subjects who received at least one dose of mirikizumab and have evaluable PK data.

All protocol deviations that occur during the study will be considered for their severity/impact and will be taken into consideration when subjects are assigned to analysis populations.

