### **11. CHANGES FROM THE PROTOCOL SPECIFIED STATISTICAL ANALYSES**

There were no changes from the protocol specified statistical analyses.

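### tmax: the plan prints the difference of observed medians beside a rank sum CI and p-value, but that CI belongs to the Hodges-Lehmann shift and can exclude the printed estimate

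*SAP*

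**What the plan says.** SAP 9.3.2 compares tmax between Test and Reference with a Wilcoxon rank sum test and then fixes the output: "Estimates of the median difference based on the observed medians, 90% CIs, and p-values from the Wilcoxon rank sum test will be calculated". Protocol 10.3.2.2 and the Statistical Analysis part of the Protocol Synopsis use the same sentence, so the documents agree with each other. The estimator (difference of observed medians) and the test are explicit. The CI method is only implied by the closing words. The example SAS code in SAP 9.3.2 covers the log-transformed Cmax and AUC model, not tmax. SAP 3 adds: "A detailed description of the planned TFLs to be presented in the clinical study report (CSR) is provided in the accompanying TFL shell document". Those shells are not part of the documents reviewed and may say more.

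SAP 9.3.1 takes tmax from observed values at actual sampling times. The Schedule of Activities puts the first post-dose PK samples on Days 3, 5, 8 and 11, with a window of one day either way from Day 5 to Day 11. Protocol 10.3.2.1 names Cmax and the two AUCs as primary and places tmax among other parameters that may be reported.

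On injection site, SAP 5 randomises "within each treatment formulation, 1:1:1 to 3 injection sites (arm, thigh, or abdomen". Site is a fixed effect for Cmax and AUC, while the overall tmax test names no stratification. Site is still visible for tmax: "PK parameters will be summarized by treatment formulation and injection site".

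**The concern.** An estimate and the interval printed beside it should come from the same procedure. Inverting the rank sum test gives limits for the Hodges-Lehmann shift. The difference of observed medians is another estimator, and nothing forces it to lie between those limits.

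The sampling scheme makes a gap more likely. Absorption peaks can be seen only at a handful of visits, so tmax clusters near 2, 4, 7 and 10 days after dose. A sample median then tends to sit on one cluster, and a few subjects can move it to the next, while the rank sum test and its CI hardly move.

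At stake is the readability of one secondary line in the report: a tmax difference of some days beside an interval that excludes it and an unremarkable p-value, or the reverse, a zero difference beside a small p-value. No primary conclusion depends on it.

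**Working it through.** **The plan's own figure.** None is given for tmax. The only stated precision concerns Cmax and AUC (SAP 7: CV 40%, 24 per formulation, 90% CI limits within 24%, probability above 90%). It reproduces: log SD = sqrt(ln(1 + 0.40²)) = 0.3853; SE = 0.3853 × sqrt(2/24) = 0.1112; half-width with 44 df = 1.6802 × 0.1112 = 0.1869; P(chi-square on 44 df ≤ 44 × (ln 1.24 / 0.1869)²) = 92.7%. Nothing below changes it.

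**Worked example (constructed).** There are 24 subjects per arm, with tmax at 2, 4 or 7 days after dose (Days 3, 5, 8). Counts at those times are Reference 5/8/11 and Test 3/8/13.

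1. Medians (mean of the 12th and 13th ordered values): Reference 4, Test 7. Printed estimate: 7 − 4 = 3 days. The arms differ only in that two more Test subjects are at 7 days and two fewer at 2.
2. All 24 × 24 = 576 Test-minus-Reference differences:

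| Difference (days) | Pairs | Running total |
|---|---|---|
| −5 | 3×11 = 33 | 33 |
| −3 | 8×11 = 88 | 121 |
| −2 | 3×8 = 24 | 145 |
| 0 | 3×5 + 8×8 + 13×11 = 222 | 367 |
| 2 | 8×5 = 40 | 407 |
| 3 | 13×8 = 104 | 511 |
| 5 | 13×5 = 65 | 576 |

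3. Hodges-Lehmann shift: the 288th and 289th differences are both 0, so the shift is 0.
4. The 90% limits are the 208th and 369th differences (exact coverage 90.3% without ties): 0 and 2.
5. Rank sum test: U = 65 + 104 + 40 + 222/2 = 320, expected 288. The tie-corrected variance is 48 × (49 − 18384/2256) = 1960.9, so SD = 44.28. Then z = (32 − 0.5)/44.28 = 0.71 and p = 0.48.

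The printed line would be 3 days, 90% CI 0 to 2, p = 0.48.

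**The opposite case.** Reference has 11 subjects at 2 and 13 at 4; Test has 13 at 4 and 11 at 7. Both medians are 4, so the printed estimate is 0. The pair differences are 0 (169), 2 (143), 3 (143) and 5 (121), so Hodges-Lehmann is 2 with 90% CI 2 to 3, and p < 0.0001.

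**Does actual timing remove it?** Clock-time scatter of up to 2.4 hours leaves the estimate in the first example outside the CI in every repeat. If the Day 5 and Day 8 visits are spread over their windows, the result depends on how. With a continuous spread over ±1 day, the estimate is outside in about 65% of draws. With shifts of −1, 0 or +1 whole day, equally likely, it is outside in about 8% or slightly fewer, by half a day or more in under 1%, and the typical printed estimate drops to about 1 day.

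**How often in general?** The documents give no absorption rates, so these figures rest on assumptions and are not bounds.

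- *480 scenarios, 2,000 trials each, 8 per formulation and site.* One-compartment SC model; half-life 10.5 days (Protocol 5.4); median absorption rate 0.25 to 1.0 per day with 30% or 50% CV; assay error 5% or 10%; several visit patterns, site effects and formulation ratios. Estimate outside the rank sum CI: median 2.7% of trials (10th to 90th percentile of scenarios 0.3 to 19%, range 0 to 55%). Outside by half a day or more: median 0.75% (0 to 8%, maximum 39%). One day or more from Hodges-Lehmann: median 14% (1.6 to 40%).
- *A second simulation* (latent tmax median 5 days, log SD 0.5, 3,000 trials per scenario). Outside in 1 to 9% of trials with visits on planned days, and under 0.5% with visits spread over the windows.

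In the 480 scenarios the Hodges-Lehmann estimate never fell outside its own CI.

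**The case against.** The strongest reply is that little is at stake and the examples are hand-built. That largely stands. They show what can happen, not how often, and the first one weakens when visits move by whole days. tmax has no hypothesis, margin or sample-size role.

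A reader might go further and infer three things that the documents do not support.

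- *Estimate, CI and p-value can never describe one quantity.* Under a pure location shift, the difference of population medians and the Hodges-Lehmann shift are the same parameter, and the rank sum test addresses it. What remains is that two sample estimators can disagree.
- *The CI might be a separate interval for the difference of medians, such as a bootstrap.* No document mentions one. The sentence follows directly on the choice of the rank sum test and ends by naming it, so the rank sum CI is the natural reading.
- *Leaving site out of the overall tmax test is an error.* Formulation is balanced over sites by design, so the unstratified test is valid. It is conservative if site shifts tmax, but Protocol 5.4 reports a site effect on bioavailability only. In the simulation, with a 1.5-fold formulation ratio in absorption rate, stratifying costs 0.6 to 3.3 power points (median 1.8) with no site effect. It breaks even at site absorption ratios of 1.25/1/0.8 (−1.9 to +2.1) and gains 0.7 to 9.0 points only at 1.5/1/0.67.

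One ambiguity does remain: the added comparison "Test versus Reference separately at each injection site (injection site will be removed from the model above" refers to a model, and tmax has none, so it is unclear whether tmax is included.

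**Conclusion.** The point holds as a low-priority improvement. Followed as written, the plan pairs an estimator with an interval and a test that belong to another estimator, and the printed difference can lie outside its own CI. The pair counts above prove this without any simulation. How often it would occur here is uncertain: it is infrequent in most assumed scenarios, with a long upper tail when visits fall on their planned days. The conclusion assumes that the CI inverts the rank sum test, and the table shells could still settle that wording. It does not touch Cmax, AUC or the sample size.

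**What to change.** In SAP 9.3.2, replace the median-difference wording for tmax with: Hodges-Lehmann estimate of the Test-minus-Reference shift, with the 90% CI that inverts the same Wilcoxon rank sum test, and observed medians by formulation shown descriptively only. Compute the limits from the numbers actually analysed, because the PK population is "all subjects who received at least one dose of mirikizumab and have evaluable PK data" and up to 60 subjects may be enrolled. They are the 208th and 369th of 576 differences for 24 v 24, and the 339th and 562nd of 900 for 30 v 30. State whether the by-site comparisons include tmax.

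SAP section 11 now reads "There were no changes from the protocol specified statistical analyses" and needs one entry for this. SAP 3 lets the SAP override the protocol's statistical text provided substantial differences are identified, so that entry should be enough.

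Cost: a short SAS step and a few sentences. The test, its p-value and its power stay the same.

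Optional: add a site-stratified (van Elteren) analysis as a sensitivity analysis, with limits computed for the actual cell sizes, since the plan expects only "approximately 8 subjects per treatment formulation and injection site". It assumes a common shift across sites, and as shown under the objection it loses about 1 to 3 power points if site does not affect tmax. It should not replace the planned tmax test.

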## 5.4. Scientific Rationale for Study Design

Conducting the study in healthy subjects mitigates the potential confounding effects of the disease state and concomitant medications in patients. A population of healthy subjects is frequently used in the assessment of the relative bioavailability of both small and large molecules.

Single doses of mirikizumab and the PK sampling time points have been selected to generate PK profiles sufficient to fulfill the study objectives.

Subjects will be randomized to receive injections in the arms, thighs, or abdomen, as injection location has been observed to have an impact on bioavailability in some studies with mirikizumab.

A parallel-group design was chosen because a crossover design is impractical for mirikizumab, which has a half-life of approximately 10.5 days. Additionally, a crossover study could confound PK data if subjects develop neutralizing antidrug antibodies (ADAs).

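### Does SAP 9.3.2 need a formulation-by-site interaction analysis alongside its separate injection-site comparisons?

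*SAP*

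**What the plan says.** The example SAS code in SAP 9.3.2 has two main effects and no product term: "model log_pk = formulation location / residual". Least-squares means are requested for formulation only, with 90% confidence limits: "lsmeans formulation / alpha=0.1 cl pdiff".

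Two further sets of comparisons follow. The first is "Test versus Reference separately at each injection site (injection site will be removed from the model above". The second is "Arm versus abdomen and thigh versus abdomen separately for each formulation (formulation will be removed from the model above". The section then adds an open clause: "Additional PK analyses may be conducted if deemed appropriate". SAP section 3 also allows supplementary analyses, to be identified in the study report.

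Protocol 5.4 gives the reason for randomising to site: "injection location has been observed to have an impact on bioavailability in some studies with mirikizumab". SAP section 7 sets the numbers at "24 subjects per treatment formulation with approximately 8 subjects per treatment formulation and injection site [arm, thigh, or abdomen". The readable text of Protocol 10.3.2.2 describes the same main-effects model and no interaction.

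**The concern.** Site is a randomised factor, chosen because it can affect bioavailability, and the SAP commits to three site-specific Test/Reference ratios. A reader who sees three ratios will ask whether they differ. The main-effects model estimates one common ratio. Each by-site fit uses about 8 against 8 subjects, and the within-formulation contrasts compare sites rather than formulations. No planned line of output is a ratio of site-specific ratios, and no interaction test is listed.

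The worry is that three wide intervals would be set side by side and chance variation read as a site-dependent formulation effect, or a real one missed. Only the interpretation of the supplementary site comparisons is at stake. The primary relative bioavailability estimate is not.

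**Working it through.** **Inputs.** CV 40%, 48 completers, 24 per formulation and about 8 per formulation-by-site cell (SAP section 7); 90% CIs (SAP 9.3.2). Log-scale SD σ = √ln(1 + 0.4²) = 0.3853. Assumed: exactly 8 per cell and the same CV in every cell.

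**The plan's own figure.** The SAP claims more than 90% probability that the 90% CI limits lie within 24% of the estimate.
- Half-width at the planning SD: h = t(0.95, df) × σ × √(2/24). With 44 df (fitted model), h = 1.6802 × 0.3853 × 0.2887 = 0.1869. With 46 df, h = 0.1867.
- The upper limit binds, at ln 1.24 = 0.2151. The probability is the chi-square CDF on df degrees of freedom at df × (0.2151/h)². With 44 df this is taken at 58.3 and gives 92.7%; with 46 df, at 61.1, it gives 93.2%.
- The claim reproduces. It concerns the overall ratio, which the site question does not touch.

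**Precision at one site.** 8 against 8, 14 df: 1.7613 × 0.3853 × √(2/8) = 0.339, a factor of 1.40 either way. The chance that such limits fall within 24% is 2.5%. The width comes from the cell size.

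**What the planned output already contains.** A by-site fit estimates the difference of two cell means on the log scale. A model with formulation, location and their product estimates the same six cell means. So:
- (Test/Reference at arm) ÷ (Test/Reference at abdomen) from the by-site fits is exactly the interaction model's point estimate.
- The second set of contrasts gives it again, as (arm/abdomen in Test) ÷ (arm/abdomen in Reference).
- The by-site ratios use disjoint subjects, so their variances add. The standard error at each site is the reported log half-width divided by 1.7613.

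**Precision of the ratio of ratios.** At the planning SD, SE = σ × √(4/8) = 0.2724.
- Two by-site fits combined (14 + 14 = 28 df): 1.7011 × 0.2724 = 0.463. The estimated SD averages 0.9911 of σ on 28 df, so the mean half-width is 0.459.
- One interaction model (42 df): 1.6820 × 0.2724 = 0.458, that is 0.63 to 1.58 around 1. The factor 0.9941 on 42 df gives a mean of about 0.456.
- The difference is negligible. In simulation the combined interval has error of about 10%, as it should.

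**Power of the 2-df interaction test at 10%.** If one site's ratio differs r-fold from the other two, the noncentrality is (2/3)(ln r)² ÷ (σ² × 2/8), with 2 and 42 df.

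| r | Noncentrality | Power |
|---|---|---|
| 1.25 | 0.89 | 20% |
| 1.5 | 2.95 | 42% |
| 2 | 8.63 | 82% |

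**Reading the intervals by overlap.** In 200,000 simulated trials with a common ratio, some pair of the three site CIs failed to overlap in 5.2%, against 10% for the interaction test. With one site 1.5-fold different the figures were 29% and 42%. This informal reading is conservative: it loses some sensitivity but does not raise false alarms.

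**The case for a change.** The strongest case for a change is that a common ratio will often produce site CIs that appear to disagree. If a reader asks only whether each CI excludes 1, then one or two of the three do so, but not all, in 27% of trials at a true common ratio of 1.0 and in 54% at 1.2, while a 10% interaction test signals falsely in 10%. A prespecified ratio of ratios with its CI would show that such patterns cannot be resolved, for a few lines of SAS.

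The arithmetic is right, but the rule behind it is not in the SAP. Section 9.3.2 sets out to estimate relative bioavailability and gives no criterion for Cmax or AUC based on whether a CI excludes 1. At a ratio of 1.0 the 27% is simply 1 − 0.9³ − 0.1³ = 0.270, the ordinary multiplicity of three 90% intervals. At 1.2 the figure is mostly partial power for a real, common effect. Neither measures mistaken claims of a site difference.

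What stands is that no direct between-site comparison is prespecified and that the open clause on additional analyses names none. Printing the ratio of ratios would be tidy. It would also bring a common-variance assumption: with CVs of 30%, 40% and 50% by site (assumed values), the pairwise intervals have error of about 6% to 14% instead of 10%. It would run on three PK parameters and need a warning about low power.

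A request for the site contrast averaged over formulations is a separate preference. It is a different estimand from the within-formulation contrasts the SAP chose.

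**Conclusion.** No change is needed. The omission is real, but it is a gap an analyst can fill from the planned output. Adjustment for location and 1:1:1 allocation already answer the reason Protocol 5.4 gives, which is that location affects bioavailability. That section does not say that the formulation ratio varies by location, and no readable objective does either (part of the objectives table is redacted, so nothing is inferred from it).

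A dedicated model would reproduce the same point estimates with a mean log half-width of about 0.456 instead of 0.459, and with power of only 20% to 42% for 1.25- to 1.5-fold differences. It would alter neither the primary ratio nor any planned comparison. If the site ratios look discrepant, the SAP already permits a supplementary analysis, which should be reported as exploratory.

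These figures assume a 40% CV in every cell and 8 completers per cell. The algebraic identity between the by-site ratios and the interaction estimate needs neither assumption.
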